9.2 Sample size determination

Sample size was determined empirically with a preliminary pilot clinical study.

10.1 Statistical effectiveness analysis

Statistical analysis of results will be performed by an independent statistician. If the statistical methods as well as the statistical settings listed above are not appropriate for newly obtained results due to specificity of variant distribution, other methods of statistical analysis will be applied. Any deviations from the statistical plan described above will be explained and justified in a protocol amendment and/or in the final report submitted to the Institutional Ethics Committee.

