Fecal specimens will be collected at the same time points by volunteers in the comfort of their homes and will be required to be delivered to the study laboratory within 1 hour of collection. All fecal specimens will be frozen and stored at the study site until analysed. Should any shipping be required the study specimens will be shipped on dry ice by overnight courier.

Among the biochemical tests conducted on serum specimens will be the activity of liver specific enzymes (alanine aminotransferase and aspartate aminotransferase as well as activity of gamma-glutamyltransferase), level of bilirubin, concentrations of triglycerides, LDL, HDL, total cholesterol and levels of peroxidation products (IOD and LDL-Px).

Biochemical assays will be performed by qualified and licensed personnel using a BioSystems Analyzer and compatible commercial kits of reagents. Standards will be purchased from Sigma-Aldrich only.

Skin swab parameters will be assessed on sebum quantity and viscosity, rate of corneocyte desquamation and damage, and total bacterial load of gram-negative bacteria.

[figure not shown]
Encoding of the results will be performed in collaboration with the Principal Investigator and the Medical Monitor.

[figure not shown]
Statistical analysis will be performed by an independent statistician using commercially available “BioStat-3” software. The statistician will not be informed of study group names or the nature of interventions in each group.

Packaging and labeling of study products and biological specimens will be carried out according to the guidelines of the NIH and US Department of Health and Human Services, as recommended for biologicals and investigational health food products. The study products will be shipped to the study site in specially designed containers with primary and secondary components. A container closure system will be used to avoid contact of investigational products with light, moisture, excess temperature and air. This packaging system guarantees stability of the products for the intended use. Protection from microbial contamination is provided by maintaining container integrity after the packaging system has been sealed. An adequate and validated procedure will be used for investigational product manufacture and packaging.

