12.2 Withdrawal of subjects due to adverse events

Any subject with adverse reaction and/or abnormal laboratory test findings will be withdrawn from the study by the Medical Officer and replaced with an eligible volunteer from the pre-screened pool of volunteers. An appropriate report to the Local Ethical Committee will be filed.

13. Statistical Methods/Data Analysis: 9.1

Study endpoint

For assessment of normally distributed parameters the Shapiro-Wilk method will be used. Student's t-test will be applied both for paired and unpaired samples. Between-group differences at one time point will be evaluated by Wilcoxon-Mann-Whitney test (continuous variables) and Fisher's Exact test (categorical variables). Data analysis will be performed using Stata SE, version 12.1. All statistical tests are two-sided and statistical significance level alpha will be set at 0.05 for the analysis.

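### Section 10.1 lets the planned tests be replaced after results are obtained, on an undefined distributional ground and with no named replacement, so the two-sided 5% level is not guaranteed

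*Protocol*

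**What the plan says.** Protocol section 13 (Statistical Methods/Data Analysis), under 9.1 Study endpoint, sets out the tests:

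- Distribution check: "For assessment of normally distributed parameters the Shapiro-Wilk method will be used".
- t-test: "Student's t-test will be applied both for paired and unpaired samples".
- Rank test: "Between-group differences at one time point will be evaluated by Wilcoxon-Mann-Whitney test (continuous variables"; Fisher's exact test is named for categorical variables.
- Settings: "All statistical tests are two-sided and statistical significance level alpha will be set at 0.05 for the analysis".

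Section 10.1 (Statistical effectiveness analysis) follows with the substitution clause. Its condition covers methods and settings alike, and its consequence is that a different method is used: "statistical settings listed above are not appropriate for newly obtained results due to specificity of variant distribution, other methods of statistical analysis". Deviations are to be "explained and justified in a protocol amendment and/or in the final report" that goes to the ethics committee. The analysis is done by an independent statistician, and the Protocol Summary (section 6) adds a safeguard: "The statistician will not be informed of study group names", nor of what each group received.

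**The concern.** Three features of section 10.1 act together.

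1. **Timing.** The trigger is a poor fit to results that have been obtained, so the decision comes after the data exist. The clause does not require it to be made before group comparisons are seen.
2. **Ground.** The distributional reason is undefined. Section 9.1 names Shapiro-Wilk but attaches no consequence to its result, and it assigns both the unpaired t-test and the Mann-Whitney test to continuous data. Two planned tests can therefore be applied to the same comparison before section 10.1 is even invoked.
3. **Control.** The and/or wording makes an explanation in the final report sufficient, with no amendment beforehand.

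The clause also mentions the settings. The only inferential settings listed above it are sidedness and alpha, so it can be read to put those in question too.

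At stake is the meaning of a reported p-value below 0.05. If the test may be settled after the results are known, the stated error rate is an intention and not a property of the design. The question can recur across several primary parameters and five arms.

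**Working it through.** **Inputs**

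- Target sample 30 (section 6); five arms (section 7.4.6, Mode of intake).
- Allocation ratio not stated. Assuming equal arms: 30 / 5 = 6 per arm.
- Two-sided alpha 0.05 (section 9.1).
- Every parameter measured at time 0 and at 1 month (section 6).
- Assumed, because the protocol gives no variances: normal data, and log-normal data with log SD 0.8 unless stated otherwise.

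**Step 1. Does a fixed test hold the plan's own 5%?** Yes.

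For the exact Mann-Whitney test at 6 v 6 there are C(12,6) = 924 equally likely rank arrangements under no effect. The counts for U = 0 to 5 are 1, 1, 2, 3, 5 and 7, which sum to 19. The attainable two-sided size is 2 × 19 / 924 = 0.041. Adding U = 6 (11 more arrangements) gives 2 × 30 / 924 = 0.065, which is over 0.05. So the size is 4.1%.

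For the t-test, 100,000 simulated null comparisons gave 4.9% (normal) and 3.6% (log-normal).

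**Step 2. Does a pre-stated distributional switch hold it?** Yes.

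The rule is: use the t-test unless Shapiro-Wilk rejects in either arm, otherwise Mann-Whitney. Over 20,000 null comparisons this gave 5.1% (normal) and 4.4% (log-normal).

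**Step 3. What if the choice is made after seeing the results?** A false positive is counted when any permitted analysis gives p < 0.05. One-sided testing in the observed direction halves the p-value, so it is counted as two-sided p < 0.10.

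| Choice made afterwards | Normal | Log-normal |
|---|---|---|
| t-test or Mann-Whitney, final value | 5.5% | 5.1% |
| t, Welch, log-scale t or Mann-Whitney, final value | 5.6% | 5.9% |
| t-test with sidedness chosen afterwards | 9.9% | 8.4% |
| t, log-scale t or Mann-Whitney, sidedness also chosen afterwards | 11.7% | 12.3% |

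Varying the log SD from 0.5 to 1.0 keeps the second row at about 6% and the last row between about 12% and 13%.

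**Step 4. What if the outcome form is also open?** With baseline-final correlation 0.5 and normal data, the best of t-test or Mann-Whitney on final value or change gives 10.1% two-sided and 20.1% with free sidedness. Section 10.1 does not grant this choice, because it speaks of methods and not of the variable analysed. Section 9.1 does not clearly settle it either. It names paired and unpaired t-tests, and refers the rank test to one time point, without saying which measure carries the between-arm comparison.

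**Step 5. Can the data verify a distributional ground?** Barely. At n = 6, Shapiro-Wilk rejects 5% of the time for normal data, 13% for log-normal with log SD 0.5 and 32% with log SD 1.0. This does not itself inflate error (step 2). It does mean that a distributional reason given afterwards could seldom be confirmed or refuted from one arm's data.

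**The case against.** The strongest reply has four parts.

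- **Alpha and sidedness are not opened.** A reader might infer that the clause lets both be replaced, so that 5% is not held even for one comparison. The text does not support that. Settings appear only in the condition, while the stated consequence is other methods. Section 9.1 makes all tests two-sided without exception. An awkward distribution is also no natural reason to change alpha or sidedness. This part stands: the reading is possible because of loose wording, but it is not what the protocol says.
- **The trigger is distribution, not significance.** Picking a test for its small p-value is not permitted, deviations must be justified, and an amendment is one of the routes. This stands as to intent. But without a threshold or a decision point, compliance cannot be checked.
- **The statistician is blinded.** This is a genuine safeguard against favouring the product, but it does not close the gap. Coded groups still yield p-values, before-after tests within a group need no arm names, and section 10.1 does not say that the blinded statistician alone decides on a change.
- **Fallback rules belong in a statistical analysis plan.** Their absence from a protocol would not be a fault. The point here is a permission that the protocol states: replacement after results, with explanation in the report enough. A separate plan could narrow it, but the protocol as written overrides its own tests.

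**Conclusion.** The two-sided 5% level is not guaranteed. It would be wrong to say that it is necessarily lost: if any switch follows distribution under a rule stated in advance, the level stays at about 4 to 5%.

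From what section 10.1 clearly permits, the exposure is about 5 to 6% per comparison, or roughly one percentage point at most over nominal. About 11 to 13% requires sidedness to be chosen afterwards as well, which is only a possible reading. The 10% and 20% figures require the outcome form to be open too. They should not be attributed to section 10.1, though section 9.1 leaves room for the question.

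All figures assume 6 per arm and the distributions stated. They are per comparison, before any multiplicity over markers and arms. The reason to act is that the change is cheap and the rule is poorly fixed, not that the demonstrated inflation is large.

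**What to change.** Amend section 10.1, with a matching line in section 9.1, to say that:

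1. Two-sided testing and alpha 0.05 do not change under any circumstances.
2. One primary between-arm analysis is named. An example is the 1-month value adjusted for the baseline already collected, log-transformed for skewed markers. This also removes the t-test/Mann-Whitney overlap and settles final value versus change.
3. Any transformation or rank-based fallback is chosen from baseline data pooled over all arms, and documented before 1-month results are opened.
4. Any method adopted later is labelled post hoc and reported beside the planned analysis, not in place of it.

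The cost is one amended paragraph, with no extra volunteers, visits or assays. The downside is less freedom to switch methods once the data arrive.

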11.1 QUALITY CONTROL AND QUALITY ASSURANCE

Independent monitoring of the clinical study for protocol and GCP compliance will be conducted periodically by Institutional Ethics Committee qualified staff from Saratov Institute of Cardiology.

Saratov Institute of Cardiology will grant direct access for the study monitors and appropriate regulatory authorities to the study data and to the corresponding source data and documents to verify the accuracy of this data.

12. DATA HANDLING AND RECORDS

12.1 Data recording/Case Report Forms

A Case Report Form (CRF) will be completed for each subject enrolled into the clinical study. The Sponsor-Investigator will review, approve and sign/date each completed CRF; the Sponsor-Investigator's signature serving as attestation of the Sponsor-Investigator's responsibility for ensuring that all clinical and laboratory data entered on the CRF are complete, accurate and authentic.

Source Data are the clinical findings and observations, laboratory and test data, and other information contained in Source Documents. Source Documents are the original records (and certified copies of original records); including, but not limited to, hospital medical records, physician or office charts, physician or nursing notes, subject diaries or evaluation checklists, dispensing records, recorded data from automated instruments, etc. Where applicable, information recorded on the CRF shall match the Source Data recorded on the Source Documents.

12.2 Record maintenance and retention

The Sponsor-Investigator will maintain records in accordance with Good Clinical Practice guidelines; to include:

- Financial disclosure information (i.e., for the Sponsor-Investigator and for sub-investigators who will be involved in the administration of the study products and/or the evaluation of research subjects [i.e., who will contribute significantly to the research study data])
- Curriculum vitae for all participants (i.e., for the Sponsor-Investigator)
- Certificates of required training; e.g., human subject protection, Good Clinical Practice, etc. (i.e., for the Sponsor-Investigator and for all sub-investigators who will be involved in the administration of the study products and/or the evaluation of research subjects [i.e., who will contribute significantly to the study data])
- Listing of printed names/signatures. (i.e., for the Sponsor-Investigator and for all sub-investigators who will be involved in the administration of the study products and/or the evaluation of research subjects [i.e., who will contribute significantly to the study data])
- Normal value(s)/range(s) for medical/laboratory/technical procedures or tests included in the clinical protocol
- Laboratory certification information
- Instructions for on-site preparation and handling of the investigational products and other study-related materials (i.e., if not addressed in the clinical protocol)
- Responsibility delegation log
- Signed informed consent forms
- Completed Case Report Forms; signed and dated by Sponsor-Investigator
- Source Documents or certified copies of Source Documents
- Monitoring visit reports
- Copies of Sponsor-Investigator correspondence (including notifications of safety information) to sub-investigators
- Subject screening and enrolment logs
- Subject identification code list

- Investigational product accountability records, including documentation of disposal.
- Final clinical study report
- Decoding procedures for blinded trials
- Master randomization list
- Retained biological specimen log
- Interim data analysis report(s)

The Sponsor-Investigator will retain the specified records and reports for up to 5 years.

13. ETHICS

13.1 Institutional Review Board (IRB) approval

The Sponsor-Investigator will obtain from the Saratov Institute of Cardiology Institutional Review Board (IRB) and Ethics Committee, prospective approval of the clinical protocol and corresponding informed consent form(s); modifications to the clinical protocol and corresponding informed consent forms, and advertisements (i.e., advertisements directed at potential research volunteers) for study recruitment.

13.2 Ethical and scientific conduct of the clinical research study

The clinical research study will be conducted in accordance with the current IRB-approved clinical protocol; ICH GCP Guidelines adopted by the FDA; and relevant policies, requirements, and regulations of Saratov Institute of Cardiology and applicable regulations of the United Kingdom and the Russian Federation Health authorities.

13.3 Subject informed consent

The Sponsor-Investigator will make certain that an appropriate informed consent process is in place to ensure that potential research subjects, or their authorized representatives, are fully informed about the nature and objectives of the clinical study, the potential risks and benefits of study participation, and their rights as research subjects. The Sponsor-Investigator, or sub-investigator(s) designated by the Sponsor-Investigator, will obtain the written, signed informed consent of each subject, or the subject's authorized representative, prior to performing any study-specific procedures on the subject. The date and time that the subject, or the subject's authorized representative, signs the informed consent form and a narrative of the issues discussed during the informed consent process will be documented in the subject's case history. The Sponsor-Investigator will retain the original copy of the signed informed consent form, and a copy will be provided to the subject, or to the subject's authorized representative.

The Sponsor-Investigator will make certain that appropriate processes and procedures are in place to ensure that any ongoing questions and concerns of enrolled subjects are adequately addressed and that the subjects are informed of any new information that may affect their decision to continue participation in the clinical study. In the event of substantial changes to the clinical study or the risk-to-benefit ratio of study participation, the Sponsor-Investigator will obtain the informed consent of enrolled subjects for continued participation in the clinical study.

14. STUDY DISCONTINUATION CRITERIA

14.1 Discontinuation of individual research subjects

Individual research subjects can be withdrawn from the study due to occurrence of adverse effects, volunteer's request (regardless of reason) or non-compliance with the protocol. Volunteers withdrawn from the study will be replaced from the pre-screened pool of volunteers.

